5.5 Breaking the Blind

Not applicable.

5.6 Subject Withdrawal

Subjects are free to withdraw from the study at any time for any reason, without affecting future medical management and treatment.

5.6.1 Reasons for Withdrawal

A subject may be withdrawn from the study by the investigator or OncoNano Medicine Inc for any of the following reasons:

- The subject develops a disease or condition that, in the opinion of the investigator, would compromise the subject's safety by continuing in the study
- The subject violates the protocol. If, in the opinion of the investigator and OncoNano Medicine, the violation is not likely to impact safety or endpoint evaluations, the investigator may permit the subject to remain in the study at the investigator's discretion and after approval by OncoNano's medical monitor. Justification for this decision should be clearly documented in source documents
- The subject becomes noncompliant or becomes uncooperative in returning for the scheduled study visits
- The subject requests withdrawal for any reason

The clinical study report will include reasons for subject withdrawals as well as details relevant to the subject withdrawal.

5.6.2 Handling of Withdrawals

If a subject withdraws prematurely from the study for any reason, study staff will make every effort to perform the Day 28 (± 5 days) assessments. The reason for subject withdrawal must be documented in the eCRF.

If a subject withdraws from the study because of an AE (clinical or laboratory), the subject will be asked to return to the clinic for, at a minimum, the evaluations scheduled. If the AE has still not resolved, additional follow-up will be performed as appropriate and documented in the subject's medical records. As a minimum requirement, AEs should be followed for 30 days after receipt of the subject's last dose of study drug, until resolution, or when judged to be stable for 30 days.

If a subject is lost to follow-up, 3 attempts (i.e., 2 phone calls, then 1 registered letter) to contact the subject will be made and documented in the subject's medical records.

5.6.3 Replacements

Withdrawn subjects may be replaced at the discretion of the sponsor.

5.6.4 Termination of Study

If, in the opinion of the investigator, the clinical observations in the study suggest that it may be unwise to continue, the investigator may terminate the study after consultation with OncoNano Medicine. A written statement fully documenting the reasons for such a termination will be provided to OncoNano Medicine. In addition, OncoNano Medicine reserves the right to discontinue the study at any time for any reason. Such a termination must be implemented by the investigator, if instructed to do so by OncoNano Medicine, in a time frame that is compatible with subjects' well-being.

If the study is terminated, all subjects will undergo a complete follow-up examination. Any clinically relevant findings, including clinically significant laboratory values and AEs, will be followed until resolution, stabilization for 30 days, or until the end of the study (the last study evaluation for the last subject), whichever occurs first.

6. STUDY VISITS

6.1 Screening and Enrollment (Days -30 to 0)

Before the study doctor can administer pegsitacianine, he/she must ensure that it is safe for the patient to be in the study vis-à-vis information that is already known about pegsitacianine. After the patient has agreed to be in the study and signed the informed consent form, the study team will perform the following procedures:

- Record their complete medical history
- Perform a complete physical examination
- Measure their weight and height and calculate a body mass index (BMI) to estimate body fat tissue
- Record vital signs (temperature, heart rate, blood pressure, and breathing rate)
- Obtain blood for routine laboratory tests, including a pregnancy test for females who are capable of becoming pregnant
- Record medications they have been taking, including prescription, over-the-counter, and herbal medications
- Determine Karnofsky Performance Status (to assess the ability to perform ordinary daily tasks)
- Confirm that the patient has met all the study criteria to participate

6.2 Pegsitacianine Administration (Days 0)

Predose procedures

- Confirm eligibility for the study and that medical information is complete
- Record weight and height and calculate BMI
- Discuss how the patient is feeling and their everyday activities
- Record vital signs
- Perform a 12-lead electrocardiogram (ECG) to check the heart activity during pre-operative screening
- Install an IV line
- Obtain blood for routine laboratory tests, including a pregnancy test for females who are capable of becoming pregnant
- Obtain blood, urine, or a breath test to test for alcohol. This test may be performed if relevant to the patient's medical history. If a urine or breath test is used and is positive, a blood test may be used to confirm the test results
- Record all medications taken since the Screening visit, including prescription, over-the-counter, and herbal medications

The Sponsor recommends the use of prophylactic diphenhydramine prior to study drug administration to decrease the possibility of an infusion-related reaction.

Dosing and postdose procedures

Procedures during and after dosing of pegsitacianine are summarized below:

- Dosing of pegsitacianine will be administered through an IV injection
Total dosing time will depend on the patient's body weight and total volume to be administered
- The following postdose assessments and procedures will occur after infusion of the study drug has been completed:
 - Record the patient's vital signs immediately after the infusion and 60 minutes afterward
 - Discuss any new or unexpected changes in how the patient is feeling
 - Record all medications they are taking, including prescription, over-the-counter, and herbal medications

6.3 Surgery and Follow-up Visits (Group 1 and 2)

Procedures at the time of cytoreductive surgery

The following procedures will be performed on the day of surgery:

- Record the patient's vital signs (only if they were abnormal at dosing)

- Obtain blood for routine laboratory tests
- Record all medications being taken, including prescription, over-the-counter, and herbal medications
- Discuss with the patient any new or unexpected changes they are feeling
- Record any AEs

Once the patient is under anesthesia, some procedures will occur that would not normally be part of surgery if the patient were not in this study. The SOC surgical procedures will be allowed to continue with the addition of the steps listed below.

- During SOC resection, the surgeon will select up to 15 (10 suspected tumor and 5 normal) specimens that will be imaged using the intraoperative camera on a section of normal tissue following excision (*Note: NIR camera should not be used to examine the peritoneal cavity at this time*)
 - A total of up to 15 specimens are to be imaged: 5 representative normal pieces of tissue and 10 individual suspected tumor specimens
 - The SOC specimens are to be resected upon the initiation of surgery and imaged on a section of normal tissue (i.e., mesentery) immediately following the collection of all SOC samples
 - The width of the camera's field of view is to be confined to a distance of 10 cm. A surgical ruler is to be placed in frame to control the width of the field of view
 - Note: while there are no specimen size stipulations provided in this protocol, the samples must be able to be imaged within the 10 cm wide imaging window.
 - For samples with multiple nodules, individual nodules should be dissected away from the bulk sample and imaged individually as single specimens.
 - Representative normal sections of tissue should be imaged in an analogous manner
- Samples will be imaged using the NIR camera and fluorescence status and specimen name will be dictated by the surgeon for documentation by the clinical research coordinator in the provided Imaging Workbook
- Once the SOC resection is complete, the surgeon will dictate their completeness of cytoreduction score to the clinical research coordinator for documentation prior to examining the peritoneal cavity with the intraoperative NIR camera in search of additional fluorescent metastatic disease that was missed during SOC
 - The peritoneal cavity will be evaluated using a manner similar to that used for

the calculation of the Peritoneal Carcinomatosis Index. Specifically, the peritoneal cavity will be examined in a methodical manner using the 13 described regions used for calculating the PCI score

- If additional fluorescent areas are to be collected, an image of the additional fluorescent lesion(s) is to be captured prior to excision from the patient
 - The camera should be held 15 cm away from the area of tissue to be excised. The camera's distance can be measured using an available surgical ruler
- Additional fluorescent lesions will then be removed and imaged on a section of normal tissue in a manner analogous to the SOC specimens with the surgeon dictating fluorescence status and specimen name to the clinical research coordinator for documentation
 - The width of the camera's field of view is to be confined to a distance of 10 cm. A surgical ruler is to be placed in frame to control the width of the field of view

Day 10 (± 5 days) or Day of Discharge (Whichever event occurs first)

- Record the patient's vital signs
- Perform 12-lead ECG to monitor heart activity
- Perform a physical examination
- Obtain blood samples for routine laboratory tests
- Record all medications being taken, including prescription, over-the-counter, and herbal medications
- Discuss any new or unexpected changes they are feeling.
- Record any AEs

Day 28 (± 5 days) after dosing

- Obtain blood samples for routine laboratory tests, including a pregnancy test for females who are capable of becoming pregnant
- Record all medications they are taking, including prescription, over-the-counter, and herbal medications
- Discuss new or unexpected changes they are feeling
- Record the patient's vital signs

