	
specimens on an area of normal tissue within the surgical field using the intraoperative NIR camera. The SOC specimens are to be resected upon the initiation of surgery and imaged on a section of normal tissue (i.e., mesentery). Specimen names and fluorescence status will be dictated by the surgeon and documented in the Imaging Workbook by the research coordinator.
 
At the conclusion of SOC resection, the intraoperative NIR camera will be used to investigate the peritoneal cavity further for evidence of residual metastases highlighted by fluorescence. Additional fluorescent specimens will be imaged in situ and then ex situ on an area of normal tissue within the surgical field prior to sending all surgical specimens to pathology for examination. The fluorescence status of each specimen will then be directly correlated to the histopathological outcomes of each specimen. This study design enables the calculation of pegasitacianine sensitivity, specificity, NPV, and PPV. Additionally, Completeness of Cytoreduction (CC) scores can be calculated following SOC resection and adjusted following the resection of additional fluorescent metastases, if warranted.

Endpoints	
Primary Endpoints:
 
 • Detection of disease left behind following SOC resection of peritoneal metastases. Detection of a single additional tumor-containing specimen excised as a result of pegasitacianine fluorescence will be deemed a clinically significant event (CSE) • Alteration to initial Completeness of Cytoreduction scores following imaging with pegasitacianine 
Secondary Endpoints:
 
 • Acceptable safety profiles following pegasitacianine administration • Sensitivity • Specificity • NPV • PPV
Study Drug	
m /k of pegasitacianine
 
prior to surgery

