	
Peritoneal Cytoreductive Surgery ; Groups 1 and 2)
 
Procedures at the time of cytoreductive surgery
 
The following procedures will be performed on the day of surgery:
 
• Record the patient's vital signs (only if they were abnormal on Day 0)• Obtain a blood sample for routine laboratory tests• Record all medications being taken, including prescription, over-the-counter, and herbal medications• Discuss with the patient any new or unexpected changes in they are feeling 
Once the patient is under anesthesia, some procedures will occur that would not normally be part of surgery if the patient were not in this study. The SOC surgical procedures will be allowed to continue with the addition of the imaging steps listed below.
 
• During SOC resection, up to 15 specimens (10 suspected tumor and 5 normal) specimens will be imaged using the intraoperative camera on a section of normal tissue• Once the SOC resection is complete, the surgeon will examine the peritoneal cavity with the intraoperative NIR camera in search of additional fluorescent metastatic disease that was missed during SOC using an assessment method similar to that used for establishing the PCI score (i.e., 13 regions)• Additional fluorescent lesions will be removed and imaged on a section of normal tissue in a manner analogous to the SOC specimens 
Day 10 (± 5 days) or Day of Discharge (Whichever event occurs first)
 
• Record the patient's vital signs• Perform 12-lead ECG to monitor heart activity• Perform a physical examination• Obtain blood samples for routine laboratory tests• Record all medications being taken, including prescription, over-the-counter, and herbal medications• Discuss any new or unexpected changes or adverse events 
Day 28 (± 5 days) after dosing
 
• Obtain blood samples for routine laboratory tests, including a pregnancy test for females who are capable of becoming pregnant• Record all medications they are taking, including prescription, over-the-counter, and herbal medications• Discuss new or unexpected changes in they are feeling• Record vital signs (temperature, heart rate, blood pressure, and breathing rate)

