3. STUDY PLAN

3.1 Overall Design

This Phase 2 study will be a an interventional, open-label, single arm trial where each patient is his/her own “intrapatient” control usin two Grou s. All patients will receive a single mg/kg dose of pegasitacianine prior to standard of care surgery.

Patients enrolled in Group 1 of the study will have a biopsy confirmed diagnosis of non-mucinous peritoneal carcinomatosis, defined as less than, or equal to 50% mucin in the sample, with a suspected Peritoneal Carcinomatosis Index (PCI) greater than or equal to . Group 2 of the study will include patients with a suspected PCI greater than or equal to and a biopsy confirmed diagnosis of mucinous peritoneal carcinomatosis, defined as > 50% mucin in the sample. A total of approximately 60 patients will be enrolled across both Groups. Enrollment will be open first to Group 1 with the opportunity to open Group 2 for enrollment following the demonstration of satisfactory pegasitacianine sensitivity and specificity values of 70% or greater in Group 1.

In both Groups 1 and 2, the surgeon will perform their SOC resection of visible metastases and image each resected specimen, and normal specimens on an area of normal tissue using the intraoperative NIR camera; no investigative NIR imaging of the peritoneal cavity will be performed at this time. The SOC specimens are to be resected upon the initiation of surgery and imaged on a section of normal tissue (i.e., mesentery). Specimen names and fluorescence status will be dictated by the surgeon and documented in the Imaging Workbook by the Clinical Research Coordinator.

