3. STUDY DESCRIPTION

3.1 Study Design

This Phase 2 study will be an interventional, open-label, single arm trial where each patient is his/her own “intrapatient” control using two Groups. All patients will receive a single █ mg/kg dose of pegsitacianine administered █ prior to standard of care surgery.

Patients enrolled in Group 1 of the study will have a biopsy confirmed diagnosis of non-mucinous peritoneal carcinomatosis, defined as less than 50% mucin in the sample, with a suspected Peritoneal Carcinomatosis Index (PCI) greater than or equal to 10. Group 2 of the study will include patients with a suspected PCI greater than or equal to 10 and a biopsy confirmed diagnosis of mucinous peritoneal carcinomatosis, defined as > 50% mucin in the sample. A total of approximately 60 patients will be enrolled across both Groups. Enrollment will be open first to Group 1 with the opportunity to open Group 2 for enrollment at the discretion of the sponsor.

In both Groups 1 and 2, the surgeon will perform their SOC resection of visible metastases and image each resected specimen, and normal specimens on an area of normal tissue outside of the surgical field using the intraoperative NIR camera; no NIR imaging of the peritoneal cavity will be performed at this time. At the conclusion of SOC resection, the intraoperative NIR camera will be used to investigate the peritoneal cavity further for evidence of residual metastases highlighted by fluorescence using an approach similar to that performed for the calculation of the Peritoneal Carcinomatosis Index (i.e., 13 regions). Additional fluorescent specimens will also be imaged on an area of normal tissue within the surgical field prior to sending all surgical specimens to pathology for examination. The fluorescence status of each specimen will then be directly correlated to the histopathological outcomes of each specimen. This study design enables the calculation of pgsitacianine sensitivity, specificity, NPV, and PPV. Additionally, Completeness of Cytoreduction (CC) scores can be calculated following SOC resection and then adjusted following the additional resection of fluorescent metastases. The schedule of events for this study is presented in [Appendix 1](#).

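### The operating surgeon reads NIR fluorescence on SOC specimens before the CC score is fixed, and the Protocol and SAP disagree on whether this happens inside the surgical field

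*Protocol*

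**What the plan says.** Protocol 3.1 describes a "single arm trial where each patient is his/her own" control. The Protocol Summary names two primary endpoints: disease left behind after SOC resection, and alteration of the initial CC score.

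On timing, the day-of-surgery schedule in the Protocol Summary states: "During SOC resection, up to 15 specimens (10 suspected tumor and 5 normal) specimens will be imaged using the intraoperative camera". Protocol 6.3 states: "The SOC specimens are to be resected upon the initiation of surgery and imaged on a section of normal tissue (i.e., mesentery) immediately following"; the sentence in full puts the imaging "immediately following the collection of all SOC samples". The surgeon dictates each specimen's fluorescence status. The CC score is dictated once SOC resection is complete, and the NIR search of the cavity follows.

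On location, the Protocol Summary (Trial Design) has the surgeon image "specimens on an area of normal tissue within the surgical field using the intraoperative NIR camera". SAP 3.1 has "normal specimens on an area of normal tissue outside of the surgical field using the intraoperative NIR camera". Protocol 3.2 refers only to a representative piece of normal tissue.

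On safeguards, Protocol 3.1 states that "no investigative NIR imaging of the peritoneal cavity will be performed at this time". Section 6.3 carries a note to the same effect and limits the view during specimen imaging to a width of 10 cm.

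**The concern.** With no second arm, the contrast rests on a clean boundary between two phases of one operation: what the surgeon finds without NIR, then what NIR adds. The person who reads the early fluorescence also decides what else to resect, when SOC is complete and what the CC score is. Fluorescence noticed on the imaging bed could lead to a lesion being resected as SOC, which removes it from the post-SOC count. It could also lead to a lesion being left for the NIR search, which adds it. The CC score before the search is open to the same influence. The study is meant to supply estimates for powering later trials (Protocol 9.1), so an unseen shift in the primary rate would carry forward.

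**Working it through.** The documents state no figure for this point, so the check compares the texts.

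1. **Order of events.** The Protocol Summary and Protocol 6.3 together give: (a) SOC specimens resected at the start; (b) up to 10 + 5 = 15 specimens imaged under NIR during SOC resection, with the surgeon calling fluorescence; (c) SOC completed; (d) CC score dictated; (e) NIR examination of the 13 regions. Step (b) precedes step (d).

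2. **Could step (b) fall at the end of SOC?** The 6.3 sentence ties imaging to the collection of all SOC samples. If that meant the whole SOC resection, imaging would come last. The reading fits poorly with imaging during SOC resection and with specimens taken at the start. Even then, 6.3 lists specimen imaging before the CC score.

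3. **Location.**
   - Protocol Summary: normal tissue within the surgical field.
   - Protocol 3.1 and 6.3: normal tissue, with mesentery named.
   - Protocol 3.2: a representative piece of normal tissue, which could be excised tissue.
   - SAP 3.1: outside the field for SOC specimens, but inside it for guided specimens.

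   The SAP takes precedence only for analyses and reporting (SAP 1), so it cannot settle how imaging is done. SAP 8 reports no planned deviations from the Protocol.

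4. **CC score wording.** Protocol 9.3 and SAP 5.1.1 say the score is documented before fluorescence imaging with the agent. Under 6.3 that is true of step (e) but not of step (b).

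5. **What the safeguards cover.** Protocol 3.1 excludes only investigative NIR imaging of the cavity; SAP 3.1 excludes any. Neither the ban nor the 10 cm view stops the surgeon from seeing fluorescence on the specimens or, if the bed is in place, on the tissue around them.

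6. **What is recorded.** The Imaging Workbook holds each specimen's name and fluorescence call. White-light and NIR images are used for intensity measurement (Protocol 9.5). SAP 7.9.5 summarises time spent imaging, and SAP 7.10.2.1 lists each specimen as SOC or fluorescence-guided. No document asks for the time of first NIR use relative to the CC score, or for a flag on lesions noticed before it.

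7. **Size.** There is no input from which to compute a shift. The planned Clopper-Pearson interval covers sampling error only. For scale, an assumed 30 responders among 60 evaluable patients gives 36.8% to 63.2%, and nothing in that interval reflects carry-over between phases.

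**The case against.** The exposure is bounded. Cavity examination with the camera is forbidden at this stage, the view is 10 cm wide, the bed is chosen as normal tissue and is partly covered by the specimen, and Protocol 3.2 may mean an excised piece. The study is an unpowered, open-label pilot. A surgeon who knows an NIR search will follow can leave tissue for it whether or not specimens were imaged early, so that upward pressure would survive any change to specimen imaging. All of this stands, and it limits the point to possible exposure rather than demonstrated bias.

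A reader might infer more than the documents support:

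- **That most of the resection is still to come when the camera is first used.** The text dates the taking of specimens, not how much surgery remains.
- **That four of the 13 regions in Appendix 3 (4/13 = 31%) are seen early.** The appendix names jejunum and ileum regions, not mesentery, and 6.3 speaks of one section of tissue in a 10 cm view.
- **That the rate shifts by a given number of points.** Any such figure only restates the share of patients assumed to change status.
- **That the control phase is free of the agent.** Every patient is dosed before surgery; what should be absent is NIR guidance.
- **That early viewing leaves no trace.** Specimen calls and images are kept; only the times and the flag are missing.

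**Conclusion.** The point holds in a limited form. By the Protocol's own order, the operating surgeon sees and calls fluorescence before the CC score is fixed, on tissue that one part of the Protocol places in the surgical field. The documents conflict on the location, and two sections describe the CC score as preceding all fluorescence imaging when it does not. The affected results are the occult-disease component of the primary endpoint and the change in CC score.

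No magnitude or direction can be given. The conclusion assumes that the SOC samples in 6.3 are the batch of up to 15. If they are the whole SOC resection, the exposure narrows to the interval just before the CC score. This is worth correcting because prevention is cheap and the planned records could not show afterwards whether carry-over occurred. It does not invalidate the study.

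**What to change.** 1. Reconcile the Protocol Summary, Protocol 3.1, 3.2 and 6.3 with SAP 3.1 so that SOC specimens are imaged away from the open cavity, as the SAP already states. Define one type of background bed for both SOC and guided specimens.
2. Record in the Imaging Workbook the time of first NIR use, the time SOC is declared complete and the time of the CC score.
3. Flag any lesion still in the patient that is first seen fluorescing before the CC score. Report the post-SOC detection rate and the CC change with and without flagged lesions.
4. Amend Protocol 9.3 and SAP 5.1.1 to say that the CC score precedes the NIR examination of the cavity.

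The cost is two or three workbook fields, one sensitivity analysis and a possible change of background tissue. The background intensity is the denominator of the specimen-to-background ratio (SBR), so summarise SBR by background type if more than one is used.

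Moving the bed does not stop the surgeon learning which specimens fluoresce, and the flag captures only what is noticed and recorded. Holding specimens until SOC ends would close more of the gap, but possibly with a long wait: Protocol 1.1 cites total surgery and HIPEC times upwards of 14 hours. Using one of the five normal specimens as the bed would take it out of the specificity set or make it its own reference. Both are optional trade-offs and should not be required.
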